5.5.2. Peripheral blood

Up to 150 mL of peripheral blood will be collected under an IRB-approved laboratory protocol (optional) for immune system monitoring described in this clinical protocol at the following time points:

- First collection: At baseline before the start of radiation therapy
- Second collection: within 7 days after completion of radiation therapy.

The treating physician or designee will have the option to cancel the laboratory protocol collection for patient safety without protocol deviation.

5.6 Rescue Medications & Supportive Care

5.6.1 Supportive Care Guidelines

Subjects should receive appropriate supportive care measures as deemed necessary by the treating investigator including but not limited to the items outlined below:

- **Diarrhea:** Subjects should be carefully monitored for signs and symptoms of enterocolitis (such as diarrhea, abdominal pain, blood or mucus in stool, with or without fever) and of bowel perforation (such as peritoneal signs and ileus). In symptomatic subjects, infectious etiologies should be ruled out, and if symptoms are persistent and/or severe, endoscopic evaluation should be considered.
 - In subjects with severe enterocolitis (Grade 3), MK-3475 will be permanently discontinued and treatment with systemic corticosteroids should be initiated at a dose of 1 to 2 mg/kg/day of prednisone or equivalent. When symptoms improve to Grade 1 or less, corticosteroid taper should be started and continued over at least 1 month.
 - In subjects with moderate enterocolitis (Grade 2), MK-3475 should be withheld and anti-diarrheal treatment should be started. If symptoms are persistent for more than one week, systemic corticosteroids should be initiated (e.g., 0.5 mg/kg/day of prednisone or equivalent). When symptoms improve to Grade 1 or less, corticosteroid taper should be started and continued over at least 1 month. Regarding guidelines for continuing treatment with MK-3475, see Section 5.2.
 - All subjects who experience diarrhea should be advised to drink liberal quantities of clear fluids. If sufficient oral fluid intake is not feasible, fluid and electrolytes should be substituted via IV infusion.
- **Nausea/vomiting:** Nausea and vomiting should be treated aggressively, and consideration should be given in subsequent cycles to the administration of prophylactic antiemetic therapy according to standard institutional practice. Subjects should be strongly encouraged to maintain liberal oral fluid intake.
- **Anti-infectives:** Subjects with a documented infectious complication should receive oral or IV antibiotics or other anti-infective agents as considered appropriate by the treating investigator for a given infectious condition, according to standard institutional practice.
- **Immune-related adverse events:** Please see Section 5.6.1.1 below and the separate guidance document in the administrative binder regarding diagnosis and management of adverse experiences of a potential immunologic etiology.
- **Management of Infusion Reactions:** Acute infusion reactions (which can include cytokine release syndrome, angioedema, or anaphylaxis) are different from

allergic/hypersensitive reactions, although some of the manifestations are common to both AEs. Signs and symptoms usually develop during or shortly after drug infusion and generally resolve completely within 24 hours of completion of infusion. Signs/symptoms may include: Allergic reaction/hypersensitivity (including drug fever); Arthralgia (joint pain); Bronchospasm; Cough; Dizziness; Dyspnea (shortness of breath); Fatigue (asthenia, lethargy, malaise); Headache; Hypertension; Hypotension; Myalgia (muscle pain); Nausea; Pruritis/itching; Rash/desquamation; Rigors/chills; Sweating (diaphoresis); Tachycardia; Tumor pain (onset or exacerbation of tumor pain due to treatment); Urticaria (hives, welts, wheals); Vomiting.

Table 5 below shows treatment guidelines for subjects who experience an infusion reaction associated with administration of MK-3475.

Table 5 Infusion Reaction Treatment Guidelines

NCI CTCAE Grade	Treatment	Premedication at subsequent dosing
Grade 1 Mild reaction; infusion interruption not indicated; intervention not indicated	Increase monitoring of vital signs as medically indicated until the subject is deemed medically stable in the opinion of the investigator.	None
Grade 2 Requires infusion interruption but responds promptly to symptomatic treatment (e.g., antihistamines, NSAIDS, narcotics, IV fluids); prophylactic medications indicated for <=24 hrs	
Stop Infusion and monitor symptoms. Additional appropriate medical therapy may include but is not limited to:
 
 IV fluids Antihistamines NSAIDS Acetaminophen Narcotics 
Increase monitoring of vital signs as medically indicated until the subject is deemed medically stable in the opinion of the investigator.
 
If symptoms resolve within one hour of stopping drug infusion, the infusion may be restarted at 50% of the original infusion rate (e.g. from 100 mL/hr to 50 mL/hr). Otherwise dosing will be held until symptoms resolve and the subject should be premedicated for the next scheduled dose.
 
Subjects who develop Grade 2 toxicity despite adequate premedication should be permanently discontinued from further trial treatment administration.
	
Subject may be premedicated 1.5h (± 30 minutes) prior to infusion of MK-3475 with:
 
Diphenhydramine 50 mg po (or equivalent dose of antihistamine).
 
Acetaminophen 500-1000 mg po (or equivalent dose of antipyretic).

Grades 3 or 4 Grade 3: Prolonged (i.e., not rapidly responsive to symptomatic medication and/or brief interruption of infusion); recurrence of symptoms following initial improvement; hospitalization indicated for other	
Stop Infusion. Additional appropriate medical therapy may include but is not limited to:
 
 IV fluids Antihistamines NSAIDS Acetaminophen Narcotics Oxygen 	No subsequent dosing

NCI CTCAE Grade	Treatment	Premedication at subsequent dosing
clinical sequelae (e.g., renal impairment, pulmonary infiltrates) Grade 4: Life-threatening; pressor or ventilatory support indicated	Pressors Corticosteroids Epinephrine Increase monitoring of vital signs as medically indicated until the subject is deemed medically stable in the opinion of the investigator. Hospitalization may be indicated. Subject is permanently discontinued from further trial treatment administration.	
Appropriate resuscitation equipment should be available in the room and a physician readily available during the period of drug administration. For Further information, please refer to the Common Terminology Criteria for Adverse Events v4.0 (CTCAE) at http://ctep.cancer.gov		

5.6.1.1 Supportive Care Guidelines for Events of Clinical Interest and Immune-related Adverse Events (irAEs) (Appendix 13.4)

Events of clinical interest of a potential immunologic etiology (irECIs) may be defined as an adverse event of unknown etiology, associated with drug exposure and is consistent with an immune phenomenon. irAEs may be predicted based on the nature of the MK-3475 compound, its mechanism of action, and reported experience with immunotherapies that have a similar mechanism of action. Special attention should be paid to AEs that may be suggestive of potential irAEs. An irAE can occur shortly after the first dose or several months after the last dose of treatment.

If an irAE is suspected, efforts should be made to rule out neoplastic, infectious, metabolic, toxin or other etiologic causes prior to labeling an adverse event as an irAE. Information on how to identify and evaluate irAEs has been developed and is included in the Event of Clinical Interest and Immune-Related Adverse Event Guidance Document located in the Administrative Binder. Subjects who develop a Grade 2 or higher irAE should be discussed immediately with the Sponsor.

Recommendations to managing irAEs not detailed elsewhere in the protocol are detailed in Table 6.

Table 6 General Approach to Handling irAEs

irAE	Withhold/Discontinue MK-3475?	Supportive Care
Grade 1	No action	Provide symptomatic treatment
Grade 2	May withhold MK-3475	Consider systemic corticosteroids in addition to appropriate symptomatic treatment
Grade 3 and Grade 4	Withhold MK-3475 Discontinue if unable to reduce corticosteroid dose to < 10 mg	Systemic corticosteroids are indicated in addition to appropriate symptomatic treatment. May utilize 1 to 2 mg/kg prednisone or equivalent per day.

	per day prednisone equivalent within 12 weeks of toxicity	Steroid taper should be considered once symptoms improve to Grade 1 or less and tapered over at least 4 weeks.
--	---	--

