2.2 Trial Diagram

- For Part A we will allow induction chemotherapy
- Primary Endpoint
 - Safety
- Secondary endpoint
 - Improvement in PFS compared to historical controls

[figure not shown]
Part A: Is only for patients with Limited Stage SCLC, we will allow induction chemotherapy. The total cycles of chemotherapy recommended will be 4, as such if a patient had two cycles of induction chemotherapy they would only get an additional two with MK-3475. PCI will be allowed based on the treating physician discretion and will be done after chemotherapy has been completed. PCI will delay the next dose of MK-3475 by one cycle and PCI should start approximately three weeks after MK-3475. MK-3475 can be resumed following the completion of PCI. LS-SCLC patients, who achieve systemic disease control during/after completion of 16 cycles of MK-3475, will be eligible to get additional 16 cycles of MK-3475, provided they did not exhibit severe (grade >3) MK-3475 related toxicity during therapy. Systemic disease control is defined as stable disease or partial response or complete response, based on irRC criteria.

Part A for LS-SCLC

* Eligible patients may receive additional 16 cycles.

Part B: Is only for patients with Extensive Stage SCLC who are receiving consolidation XRT after 1-6 cycles of chemotherapy. Patients needing PCI are encouraged to have it completed prior to enrollment in this trial. If PCI needs to be given on study, after thoracic XRT, then it should be done in a manner consistent with part A. PCI will delay the next dose of MK-3475 by one cycle and PCI should start approximately three weeks after MK-3475. MK-3475 can be resumed following the completion of PCI.) Patients needing XRT treatment to other sites outside the thorax will be allowed, but is encouraged to be done prior to starting the trial.

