5.2.1.2 Dose Modification

MK-3475 will be withheld for drug-related Grade 4 hematologic toxicities, non-hematological toxicity \geq Grade 3 including laboratory abnormalities, and severe or life-threatening AEs as per Table 3 below.

Table 3: Dose modification guidelines for drug-related adverse events.

Toxicity	Grade	Hold Treatment (Y/N)	Timing for restarting treatment	Dose/Schedule for restarting treatment	Discontinue Subject (after consultation with Sponsor)
Hematological Toxicity	1, 2, 3	No	N/A	N/A	N/A
	4	Yes	Toxicity resolves to Grade 0-1 or baseline	May increase the dosing interval by 1 week	Toxicity does not resolve within 12 weeks of last infusion Permanent discontinuation should be considered for any severe or life-threatening event
Non-hematological toxicity	1	No	N/A	N/A	N/A
	2	Consider withholding for persistent symptoms	Toxicity resolves to Grade 0-1 or baseline	Clinical AE resolves within 4 weeks: Same dose and schedule (reference Section 5.6.1.2 for recommendations regarding pneumonitis) Clinical AE does not resolve within 4 weeks: May increase the dosing interval by 1 week for each occurrence	Toxicity does not resolve within 12 weeks of last infusion

Note: Exception to be treated similar to grade 1 toxicity

- Grade 2 alopecia
- Grade 2 fatigue

For additional information regarding Adverse Events with a potential Immune-Etiology reference Section 5.6.1.1.

Toxicity	Grade	Hold Treatment (Y/N)	Timing for restarting treatment	Dose/Schedule for restarting treatment	Discontinue Subject (after consultation with Sponsor)
	3, 4	Yes	Toxicity resolves to Grade 0-1 or baseline	May increase the dosing interval by 1 week for each occurrence	Toxicity does not resolve within 12 weeks of last infusion Permanent discontinuation should be considered for any severe or life-threatening event

In case toxicity does not resolve to Grade 0-1 within 12 weeks after last infusion, trial treatment should be discontinued after consultation with the Sponsor. With investigator and Sponsor agreement, subjects with a laboratory adverse event still at Grade 2 after 12 weeks may continue treatment in the trial only if asymptomatic and controlled. For information on the management of adverse events, see Section 5.6.1.

Subjects who experience a recurrence of the same severe or life-threatening event at the same grade or greater with re-challenge of MK-3475 should be discontinued from trial treatment.

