5.8 Subject Withdrawal/Discontinuation Criteria

Subjects may withdraw consent at any time for any reason or be dropped from the trial at the discretion of the investigator should any untoward effect occur. In addition, a subject may be withdrawn by the investigator or the Sponsor if enrollment into the trial is inappropriate, the trial plan is violated, or for administrative and/or other safety reasons. Specific details regarding discontinuation or withdrawal are provided in Section 7.1.3 – Other Procedures.

A subject must be discontinued from the trial for any of the following reasons:

- The subject or legal representative (such as a parent or legal guardian) withdraws consent.
- Confirmed radiographic disease progression

Note: For unconfirmed radiographic disease progression, please see Section 5.2.2

Note: A subject may be granted an exception to continue on treatment with confirmed radiographic progression if clinically stable or clinically improved, please see Section 7.1.2.7.1

- Unacceptable adverse experiences as described in Section 5.2.1.2
- Intercurrent illness that prevents further administration of treatment
- Investigator's decision to withdraw the subject
- The subject has a confirmed positive serum pregnancy test
- Noncompliance with trial treatment or procedure requirements
- The subject is lost to follow-up
- Completed 24 months of treatment with MK-3475

Note: 24 months of study medication is calculated from the date of first dose. Subjects who stop MK-3475 after 24 months may be eligible for up to one year of additional study treatment if they progress after stopping study treatment provided they meet the requirements detailed in Section 7.1.5.2.1.

- Administrative reasons

The End of Treatment and Follow-up visit procedures are listed in Section 6 (Protocol Flow Chart) and Section 7.1.5 (Visit Requirements). After the end of treatment, each subject will be followed for 30 days for adverse event monitoring (serious adverse events will be collected for 90 days after the end of treatment as described in Section 7.2.3.1). Subjects who discontinue for reasons other than progressive disease will have post-treatment follow-up for

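### Section 5.6.1 requires a permanent stop for grade 3 enterocolitis, Table 3 allows restart, and no text ranks the two; grade 4 is left to the more lenient rule

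*Combined protocol and SAP*

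**What the plan says.** **Event-specific rule.** Under diarrhea, Section 5.6.1 states: "In subjects with severe enterocolitis (Grade 3), MK-3475 will be permanently discontinued and treatment with systemic corticosteroids should be initiated". The next bullet, on grade 2, withholds the drug and sends the reader back for the restart rules: "Regarding guidelines for continuing treatment with MK-3475, see Section 5.2". The grade 3 bullet has no such referral. Grade 4 enterocolitis is not mentioned.

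**General rule.** In Section 5.2.1.2, Table 3 handles every drug-related non-hematological event of grade 3 or 4 in one row. The drug is held, and may restart when the event is back to grade 0-1 or baseline. On restart the row says: "May increase the dosing interval by 1 week for each occurrence". A permanent stop follows if the event has not resolved within 12 weeks of the last infusion. Otherwise: "Permanent discontinuation should be considered for any severe or life-threatening event". The text below the table plainly expects that some patients will be re-challenged, because it orders discontinuation for this group: "Subjects who experience a recurrence of the same severe or life-threatening event at the same grade or greater with re-challenge of MK-3475".

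**Links between the two.** The text after Table 3 refers to 5.6.1 for managing adverse events and to 5.6.1.1 for immune-related ones. The mandatory discontinuation list in Section 5.8 includes: "Unacceptable adverse experiences as described in Section 5.2.1.2". It does not name 5.6.1.

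**Appendix 13.4.** Section 3.2 of the guidance document says to hold at grade 3 and to discontinue permanently at grade 4. Section 1 of that document tells the reader to follow the protocol's own language on dose modification.

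**The concern.** For a grade 3 enterocolitis that resolves within 12 weeks, one section forbids further MK-3475 and the section titled Dose Modification permits it. A rule that a drug must be stopped for good should not depend on the reader choosing the right principle of interpretation. Grade 4 is the odder case. Section 5.6.1 is silent there, so the worse event gets the more lenient rule in the protocol body.

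At stake is the safety of an individual patient who is re-challenged after severe bowel toxicity. What could differ in the data is exposure, the number of discontinuations, and any recurrent event entering the adverse event tables of Section 9.2.3.

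**Working it through.** The plan gives no figure to reproduce here. The check sets the texts side by side and then bounds the exposure.

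| Text | Grade 3 enterocolitis | Grade 4 enterocolitis |
|---|---|---|
| 5.6.1, diarrhea bullets | Permanent stop | Not named |
| 5.2.1.2, Table 3 | Hold; restart allowed at grade 0-1 or baseline; stop if unresolved at 12 weeks | Same row, same rule |
| 5.6.1.1, Table 6 (irAEs not covered elsewhere) | Should not apply, since 5.6.1 covers it | Withhold; stop if steroids cannot be reduced below 10 mg/day within 12 weeks |
| Appendix 13.4, section 3.2 | Hold | Permanent stop |
| Appendix 13.4, section 1 | Defers to protocol | Defers to protocol |

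**Step 1, when the rules diverge.** If the event is unresolved at 12 weeks, both sections end treatment. They part only when it resolves within 12 weeks.

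**Step 2, is there a ranking?** The pointer from 5.2.1.2 to 5.6.1 tells the reader where to find management advice, not which rule wins. Table 3's grade 2 row does cite 5.6.1.2 for pneumonitis, but its grade 3-4 row has no comparable exception. The only ranking found places the protocol above the appendix. It does not rank two protocol sections against each other.

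**Step 3, grade 4.** Because the appendix defers to the protocol, its permanent stop at grade 4 yields, on a literal reading, to Table 3.

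**Step 4, other events on the same row.** For grade 3-4 infusion reactions, Table 5 says: "Subject is permanently discontinued from further trial treatment administration". Table 7 likewise discontinues for grade 3-4 pneumonitis. The same Table 3 row would allow restart after either, so one override line should cover all three.

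**Step 5, ceiling on exposure.** Inputs are 16 cycles (Table 2), one dose per cycle, and the event following dose 1.
- Under 5.6.1: 0 further doses.
- Under Table 3: 16 - 1 = 15 further doses.
- Fit with the 24-month limit in Section 5.8 (about 104 weeks): with dose 2 as late as week 12, 14 more doses every 3 weeks end at 12 + 14 x 3 = week 54. Every 4 weeks, they end at 12 + 14 x 4 = week 68. Both fit.

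**Step 6, statistical figures.** The DLT definition and the grading of the index event do not depend on whether the drug is later restarted. The sample-size statements in Section 9.2.5 do not use it either.

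**The case against.** The strongest reply is that the two rules can be obeyed together. Table 3 is general and permissive, 5.6.1 is specific and mandatory, and stopping satisfies both. The structure of 5.6.1 supports this, because only its grade 2 bullet sends the reader back to Section 5.2. Section 5.2.1.2 itself directs the reader to 5.6.1, so a site that restarts on Table 3 alone has not followed that reference. This stands as the better reading for grade 3, and it is why the point is minor. It remains an inference, and it does not help at grade 4, where 5.6.1 has no rule to prefer.

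There are also safeguards. Section 5.6.1.1 requires immediate discussion with the Sponsor of any irAE of grade 2 or higher. Section 7.2.3.2 requires 24-hour reporting of grade 3 or higher diarrhea or colitis. Table 10 requires advance approval before re-challenge after a serious event that the drug may have caused. These make an unnoticed re-challenge less likely. None withdraws Table 3's permission, and the Table 10 approval is itself tied to the dose modification guidelines.

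A reader might infer a larger ceiling from the Part A extension in Section 2.2, under which patients "will be eligible to get additional 16 cycles of MK-3475, provided they did not exhibit severe (grade >3) MK-3475 related toxicity during therapy". Taken literally, a grade 3 event would not bar extension, giving 16 + 16 - 1 = 31 further doses. The documents do not support relying on that. Section 5.6.1 and Table 10 both use the word severe for grade 3, so the inequality in Section 2.2 conflicts with its own adjective and is probably a slip for grade 3 or higher. On that reading the patient is barred from extension and 15 stands.

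**Conclusion.** The inconsistency is real and small. Section 5.6.1 and Table 3 give different outcomes for a resolved grade 3 enterocolitis, no sentence settles which governs, and grade 4 is left to the row that allows restart. The consequence is possible re-challenge of an individual patient, with a ceiling of 15 further doses against 0. That ceiling assumes that the event follows dose 1, resolves within 12 weeks, and is followed by every remaining planned cycle. It is not an expected effect, and the documents give no frequency for the event.

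Two stronger conclusions should not be drawn. A reader might infer that dose escalation or the safety conclusions are compromised, but the DLT count and the statistical figures are unaffected. A reader might also infer that the grade 3 hold in Appendix 13.4 is a third competing rule. It is not, because the appendix defers to the protocol.

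This is a minor safety-consistency correction.

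**What to change.** Make three wording changes in the protocol body:

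1. Add to the grade 3-4 non-hematological row of Table 3: *Event-specific rules in 5.6.1 (enterocolitis), Table 5 (infusion reactions) and Table 7 (pneumonitis) override this restart rule.*
2. In Section 5.6.1, extend the permanent-stop bullet to *severe enterocolitis (Grade 3 or 4)*. This agrees with the appendix's existing grade 4 rule.
3. In the Section 5.8 list, cite 5.6.1 beside 5.2.1.2.

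Leave Appendix 13.4 as it is. It is a program-wide guidance document with its own version history and already gives way to the protocol.

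The cost is a wording amendment only, with no change to the design, sample size, data collection or analysis.

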5.6.1.2 Supportive Care Guidelines for Pneumonitis

Subjects with symptomatic pneumonitis should immediately stop receiving MK-3475 and have an evaluation. The evaluation may include bronchoscopy and pulmonary function tests to rule out other causes such as infection. If the subject is determined to have study drug associated pneumonitis, the suggested treatment plan is detailed in Table 7.

Table 7 Recommended Approach to Handling Pneumonitis

Study drug associated pneumonitis	Withhold/Discontinue MK-3475?	Supportive Care
Grade 1 (asymptomatic)	No action	Intervention not indicated
Grade 2	Withhold MK-3475, may return to treatment if improves to Grade 1 or resolves within 12 weeks	Systemic corticosteroids are indicated. Taper if necessary.
Grade 3 and Grade 4	Discontinue MK-3475	Systemic corticosteroids are indicated. The use of infliximab may be indicated as appropriate. Refer to the Event of Clinical Interest and Immune-related Adverse Event Guidance Document for additional recommendations.

For Grade 2 pneumonitis that improves to \leq Grade 1 within 12 weeks, the following rules should apply:

- First episode of pneumonitis
 - May increase dosing interval by one week in subsequent cycles
- Second episode of pneumonitis – permanently discontinue MK-3475 if upon rechallenge subject develops pneumonitis \geq Grade 2

